7.0 Protocol Treatment

7.1 Treatment Schedule

7.11 Phase I Component:

- Lenalidomide at assigned dose (Section 7.21, Tables 7.211, 7.212 or 7.213)
- Dexamethasone 40 mg orally on days 1, 8, 15 and 22
- Anticoagulation (see Section 9.4)

Dosing for lenalidomide for each group is per the assigned cohort; see tables in Section 7.21. Each cycle is 28 days. All groups get a 7 day rest (days 22-28) from lenalidomide. Dosing will be in the morning at approximately the same time each day. Only one cycle of study drug will be supplied to the patient each cycle. Lenalidomide capsules should be swallowed whole, and should not be broken, chewed or opened. If a dose of lenalidomide is missed, it should be taken as soon as possible on the same day. If it is missed for the entire day, it should not be made up (this applies to all dosing schedules). For patients in Group C, when a lenalidomide treatment day occurs on a dialysis day, lenalidomide must be taken after dialysis. Patients who take more than the prescribed dose of lenalidomide should be instructed to seek emergency medical care if needed and contact study staff immediately.

Compliance with therapy will be assessed at the beginning of each cycle and at the end of treatment. Patients will be given a medication diary for recording of doses of study drugs as provided by each study site.

Dexamethasone will be given at a fixed dose of 40 mg by mouth once weekly on a 28 day treatment cycle. If a dose of dexamethasone is missed, it is up to the treating physician whether the dose should be made up. In addition, continuing dexamethasone if lenalidomide is stopped is also at the discretion of the treating physician.

Treatment is to be continued as tolerated until disease progression, intolerable toxicity or patient refusal.

Subjects experiencing adverse events may need study treatment modifications.

If patient is treated beyond 4 cycles, therapy may be interrupted to allow for stem cell harvest and mobilization.

7.111 Phase I Dose Assignment

We want to determine the MTD for patients with MM in three different risk groups:

- Moderate Renal Dysfunction (30-60 CrCl mL/min)
- Severe Renal Dysfunction (CrCl <30 mL/min, not requiring dialysis)
- ESRD Renal Dysfunction (CrCl <30 mL/min, requiring hemodialysis or peritoneal dialysis)

7.112 Creatinine Clearance will be estimated by using the Cockcroft and Gault equation (see Appendix IV):

Males:

$$\text{CrCl (mL/min)} = \frac{(140 - \text{age}) \times (\text{weight, kg})}{72 \times (\text{serum creatinine, mg/dL})}$$

Females:

$$\text{CrCl (mL/min)} = \frac{(140 - \text{age}) \times (\text{weight, kg})}{72 \times (\text{serum creatinine, mg/dL})} \times 0.85$$

If the patient is >65 y/o and creatinine is <1, use 1 as serum creatinine value to calculate the creatinine clearance.

7.12 Phase II Component:

- Lenalidomide at assigned dose (as determined by studies in Phase 1 component)
- Dexamethasone 40 mg orally on days 1, 8, 15 and 22
- Anticoagulation (see Section 9.4)

The dose for lenalidomide will be determined for each group in the Phase 1 portion of the study. Each cycle is 28 days. All groups get a 7 day rest (days 22-28) from lenalidomide. Dosing will be in the morning at approximately the same time each day. Only one cycle of study drug will be supplied to the patient each cycle. Lenalidomide capsules should be swallowed whole, and should not be broken, chewed or opened. If a dose of lenalidomide is missed, it should be taken as soon as possible on the same day. If it is missed for the entire day, it should not be made up (this applies to all dosing schedules). For patients in Group C, when a lenalidomide treatment day occurs on a dialysis day, lenalidomide must be taken after dialysis. Patients who take more than the prescribed dose of lenalidomide should be instructed to seek emergency medical care if needed and contact study staff immediately.

Dexamethasone will be given at a fixed dose of 40 mg by mouth once weekly on a 28 day treatment cycle. If a dose of dexamethasone is missed, it is up to the treating physician whether the dose should be made up. In addition, continuing dexamethasone if lenalidomide is stopped is also at the discretion of the treating physician.

Treatment is to be continued as tolerated until disease progression, intolerable toxicity or patient refusal.

7.2 Phase I Dose Escalation and Determination of MTD.

7.21 Dose Escalation of Lenalidomide:

Table 7.211: Group A = Patients with a 30-60 CrCl (mL/min)[□]

Dose Level		Dose	Treatment Day	Rest Day	Route
1*	Lenalidomide	10 mg	1-21	22-28	Orally
2	Lenalidomide	15 mg	1-21	22-28	Orally
3	Lenalidomide	25 mg	1-21	22-28	Orally

Table 7.212: Group B = Patients with CrCl <30 mL/min who are NOT on dialysis[△]

Dose Level		Dose	Treatment Day	Rest Day	Route
1*	Lenalidomide	15 mg	Every other day, days 1-21	22-28	Orally
2	Lenalidomide	25 mg	Every other day, days 1-21	22-28	Orally
3	Lenalidomide	15 mg	1-21	22-28	Orally
4	Lenalidomide	25 mg	1-21	22-28	Orally

Table 7.213: Group C = Patients with CrCl <30 mL/min who are on dialysis^{#◊}

Dose Level		Dose	Treatment Day	Rest Day	Route
1*†	Lenalidomide	5 mg	1-21 [£]	22-28	Orally
2	Lenalidomide	10 mg	1-21 [£]	22-28	Orally
3	Lenalidomide	15 mg	1-21 [£]	22-28	Orally
4	Lenalidomide	25 mg	1-21 [£]	22-28	Orally

* Starting dose level

Dialysis includes hemodialysis or peritoneal dialysis.

† The starting dose for patients in Group C accrued to dose level 1 cohort (completed September 2010) was lenalidomide 15 mg post dialysis three times weekly on Days 1-21. Starting with protocol version 5.0, if a return to dose level 1 is indicated, lenalidomide 5 mg on Days 1-21 should be used according to the package insert.

£ When a lenalidomide treatment day occurs on a dialysis day, lenalidomide must be taken after dialysis.

□ Group A: As of November 03, 2010, dose level 1 is completed. Dose level 2 is open.

△ Group B: As of November 03, 2010, dose level 1 is completed. Dose level 2 is open.

◊ Group C: As of November 03, 2010, dose level 1 is completed. Dose level 2 is open.

7.22 Definition of Dose-Limiting Adverse Events

Dose Limiting Adverse Events:

Dose Limiting Toxicity (DLT) will be defined as any of the following events that is determined to be possibly, probably, or definitely related to lenalidomide (as determined by the investigator) within the first cycle of therapy irrespective of whether the adverse events resolved:

- Grade 3 or higher neutropenia with fever $\geq 38.5^{\circ}\text{C}$
- Grade 4 neutropenia ≥ 7 days
- Grade 4 or higher thrombocytopenia
- Other non-hematologic Grade 4 or higher adverse event not present prior to starting therapy or not due to underlying cause

Management and dose modifications associated with the above AEs are outlined in Section 8.0.

7.23 Dose Escalation Phase:

A standard cohort of 3 phase I design will be used where subjects will be initially enrolled in groups of three and individually assessed for safety and DLT. For a subject to be considered evaluable for dose limiting toxicity the subject must have received at least one dose of both drugs in Cycle 1 and have not been withdrawn from the study prior to Cycle 2 secondary to a drug related AE. If a subject withdraws from the study without meeting these criteria for reasons other than adverse events, the subject will be replaced in that cohort.

Doses will be escalated until the first observation of a DLT as defined in Section 7.22 in the first treatment cycle in a group of at least 3 subjects treated at that dose level. All DLTs occurring in the first 3 cycles of the Phase I and II components will be collected and considered in the overall analysis, however, only DLTs occurring in Cycle 1 will define MTD during the Phase I component. Severity grading will be defined using National Cancer Institute Common Terminology Criteria for Adverse Events (NCI CTCAE V4.0). A one-time dose escalation of lenalidomide after 2 cycles of treatment due to improvement of renal function is allowed within an individual patient as described in Section 8.3.

A standard 3+3 phase I design will be used to determine the recommended dose in each renal dysfunction group. Dose level 1 will be the initial dose level (see Tables in Section 7.21).

- For current dose level accrue 3 patients (accrual for the group [Group A, B, or C] will be temporarily closed while the 3 patients are evaluated for DLT).
- If exactly 0/3 experience a DLT, then proceed to the next higher dose level.

- If exactly 1/3 experience a DLT, then accrue 3 more patients at the current dose level (accrual for the group [Group A, B, or C] will be temporarily closed while the 3 additional patients are evaluated for DLT). If (out of 6 patients) there are at least 2 that experienced a DLT, the recommended dose level has been exceeded. Drop down one dose level.
- If 2 or more (out of 3) patients experience a DLT, the recommended dose level has been exceeded. Drop down one dose level.

The recommended dose level for the phase II portion of the trial is the maximum dose level that resulted in less than 2/6 patients with DLTs. Patients who experience DLTs will be dose reduced to the next lower dose level.

Dose escalation will proceed within each group [Group A, B, or C] according to the following scheme. A DLT is defined above.

Number of Patients with DLT at a Given Dose Level	Phase I Escalation Decision Rule
0 out of 3	Enter 3 patients at the next dose level.
≥ 2	Dose escalation will be stopped. This dose level will be declared the maximally administered dose (highest dose administered). Three (3) additional patients will be entered at the next lowest dose level if only 3 patients were treated previously at that dose.
1 out of 3	Enter at least 3 more patients at this dose level. 
 • If 0 of these 3 patients experience DLT, proceed to the next dose level. • If 1 or more of this group suffer DLT, then dose escalation is stopped, and this dose is declared the maximally administered dose. Three (3) additional patients will be entered at the next lowest dose level if only 3 patients were treated previously at that dose.
≤ 1 out of 6 at highest dose level below the maximally administered dose	This is generally the recommended phase 2 dose. At least 6 patients must be entered at the recommended phase 2 dose.

Once the MTD is reached in the Phase I component for Group A, B or C, the group with the defined MTD dose will immediately be eligible to go to the Phase II component, and will not have to wait for the MTD in the other two groups

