8.3 Lenalidomide Dose Modification Based On Non-Hematological Toxicity (see Table 8.31)

A one-time dose escalation in lenalidomide of one dose level is allowed at any one time point after completion of 2 cycles of treatment if one of the following conditions is met:

1. The patient was originally registered in Group C but has renal function improvement to a point that dialysis is no longer needed; or
2. The patient was originally registered in Group B but has renal function improvement to $\geq 30 \text{ CrCl (mL/min)}$.

All previously established or new toxicities observed any time, are to be managed as per Table 8.31 and Table 8.4.

If drug must be discontinued, the patient comes off treatment and goes to follow-up per Section 4.0 and event monitoring per eCRF completion guidelines. If the toxicity resolves and drug is to be restarted, the dose must be reduced by dose levels as indicated in the dose reduction table.

Please note: Held doses are not made up.

Table 8.31: Dose Modification for Lenalidomide

NCI CTC Toxicity Grade	Day 2-14 of Cycle	≥Day 15 of Cycle
Grade 3 neutropenia associated with fever (temperature $\geq 38.5^{\circ}\text{C}$) or Grade 4 neutropenia	
 Hold lenalidomide. Follow CBC weekly. If neutropenia has resolved to \leqgrade 2, restart at next lower dose level and continue the cycle until day 21. 	
 Hold lenalidomide for remainder of cycle. Restart lenalidomide next cycle (decrease dose by one dose level).
Thrombocytopenia \geq Grade 3 (platelet count $< 50,000/\text{mm}^3$)	
 Hold lenalidomide. Follow CBC weekly. If thrombocytopenia resolves to \leqgrade 2, restart lenalidomide at next lower dose level and continue the cycle through Day 21. 	
 Hold lenalidomide for remainder of cycle. Restart lenalidomide next cycle (decrease dose by one dose level).
Non-blistering rash Grade 3	
 If Grade 3, hold lenalidomide dose. Follow weekly. If the adverse event resolves to \leqgrade 1, restart lenalidomide at next lower dose level and continue the cycle through Day 21. 	
 Hold lenalidomide for remainder of cycle. Restart lenalidomide next cycle (decrease dose by one dose level).

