Grade 4	
 Discontinue lenalidomide study drug and go to follow-up and event monitoring. 	
 Discontinue lenalidomide study drug and go to follow-up and event monitoring.
Desquamating (blistering) rash- any Grade	
 Discontinue lenalidomide study drug and go to follow-up and event monitoring. 	
 Discontinue lenalidomide study drug and go to follow-up and event monitoring.
Erythema multiforme \geq Grade 3	
 Discontinue lenalidomide study drug and go to follow-up and event monitoring. 	
 Discontinue lenalidomide study drug and go to follow-up and event monitoring.
Sinus bradycardia/other cardiac arrhythmia Grade 2 \geq Grade 3	
 Hold lenalidomide dose. Follow at least weekly. If the adverse event resolves to \leqgrade 1, restart lenalidomide at next lower dose level and continue the cycle through Day 21. 	
 Hold lenalidomide for remainder of cycle. Restart lenalidomide next cycle (decrease dose by one dose level).
	
 Discontinue lenalidomide study drug and go to follow-up and event monitoring. 	
 Discontinue lenalidomide study drug and go to follow-up and event monitoring.

Allergic reaction or hypersensitivity Grade 2-3	
 Hold lenalidomide dose. Follow at least weekly. If the adverse event resolves to \leqgrade 1, restart lenalidomide at next lower dose level and continue the cycle through Day 21. 	
 Hold lenalidomide for remainder of cycle. Restart lenalidomide next cycle (decrease dose by one dose level).
Grade 4	
 Discontinue lenalidomide study drug and go to follow-up and event monitoring. 	
 Discontinue lenalidomide study drug and go to follow-up and event monitoring.
Venous thrombosis/embolism \geq Grade 3	
 Hold lenalidomide and start therapeutic anticoagulation; restart lenalidomide at investigator's discretion (maintain dose level). 	
 Hold lenalidomide for remainder of cycle. See Anticoagulation Consideration (see Section 9.4). Restart lenalidomide next cycle (decrease dose by one dose level).

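### Section 7.23, read literally, leaves a patient withdrawn because of a Cycle 1 DLT neither evaluable nor replaced, which conflicts with the 3+3 rules and with Sections 16.12, 13.6 and 16.11

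*Protocol*

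**What the plan says.** Section 7.23 is the only place in either document that says who is evaluable for DLT. It sets two conditions: the patient took each of the two drugs at least once in Cycle 1, and must "have not been withdrawn from the study prior to Cycle 2 secondary to a drug related AE". The next sentence deals with replacement. If a patient leaves "without meeting these criteria for reasons other than adverse events, the subject will be replaced in that cohort".

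The text around it counts differently:

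- Section 7.22 defines a DLT by type of event, relation to lenalidomide and timing: "within the first cycle of therapy irrespective of whether the adverse events resolved".
- The 3+3 rules in Section 7.23 work on patients who have a DLT. "If exactly 0/3 experience a DLT, then proceed to the next higher dose level". After expansion: "If (out of 6 patients) there are at least 2 that experienced a DLT", the dose is too high.
- Section 16.12 sets the MTD from the same count, with a threshold of 2 among at most 6 patients.
- Section 13.6 makes a phase I patient inevaluable, and replaces that patient, when Cycle 1 is not completed for a cause that is not toxicity. Section 16.11 and SAP 8.1 describe replacement in the same terms.
- Section 13.4 lists an adverse event among the reasons for which a patient may be withdrawn.

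**The concern.** Take a patient who has a DLT in Cycle 1 and is withdrawn from the study because of it. Under the literal evaluability sentence this patient is not evaluable for DLT. Under the replacement sentence the place is not refilled, because the exit was for an adverse event. Yet this is exactly the patient whom a 3+3 design has to count. Sections 13.6 and 16.11 run the other way: they set aside non-toxicity exits only.

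The count at stake decides escalation, and so the MTD in each of the three renal groups, which is the phase I primary objective. It also fixes the dose carried into phase II. With cohorts of 3, the classification of one patient can change the decision.

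**Working it through.** **Inputs.** p is the true DLT rate, taken at the values in Section 16.14. f is the share of Cycle 1 DLTs that end in study withdrawal before Cycle 2. The documents do not give f, so it is assumed at 5%, 10% and 25%. The escalation rule is that of Section 7.23: escalate on 0 of 3, or on 1 of 3 followed by 0 of the next 3.

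**Step 1: the plan's own figures, every DLT counted.** P(escalate) = (1−p)³ + 3p(1−p)²·(1−p)³ = (1−p)³ + 3p(1−p)⁵.

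| p | Computed | Section 16.14 |
|---|---|---|
| 0.10 | 0.906 | 0.91 |
| 0.20 | 0.709 | 0.71 |
| 0.30 | 0.494 | 0.49 |
| 0.40 | 0.309 | 0.31 |
| 0.50 | 0.172 | 0.17 |

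All five entries reproduce.

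**Step 2: three ways to handle a withdrawn DLT patient.**

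- *Stalled.* The patient is non-evaluable and not replaced, and an incomplete cohort does not license escalation: (1−p)³ + 3p(1−f)(1−p)⁵. This is closest to the text, since the rules have no row for a cohort with fewer than 3 evaluable patients.
- *Dropped and refilled.* The Step 1 formula with q = p(1−f)/(1−pf) in place of p.
- *Scored DLT-free.* The Step 1 formula with q = p(1−f) in place of p.

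Worked example, p = 0.4 and f = 0.25:

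- Stalled: 0.216 + 3(0.4)(0.75)(0.07776) = 0.216 + 0.070 = 0.286.
- Refilled: q = 0.30/0.90 = 0.333, giving 0.296 + 0.132 = 0.428.
- DLT-free: q = 0.30, giving 0.494.

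| p (stated probability) | f | Stalled | Refilled | DLT-free |
|---|---|---|---|---|
| 0.40 (0.31) | 5% | 0.305 | 0.330 | 0.343 |
| | 10% | 0.300 | 0.351 | 0.378 |
| | 25% | 0.286 | 0.428 | 0.494 |
| 0.30 (0.49) | 5% | 0.487 | 0.516 | 0.525 |
| | 10% | 0.479 | 0.539 | 0.557 |
| | 25% | 0.456 | 0.614 | 0.654 |

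At f = 0 all three return the stated value.

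**Step 3: how often the case would arise.** The chance that a first cohort of 3 holds at least one such patient is 1 − (1−pf)³. At p = 0.4 this is 0.059, 0.115 and 0.271 for f = 5%, 10% and 25%.

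Withdrawals for a toxicity that is not a DLT are not modelled.

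**The case against.** The strongest reply is that no decision rule refers to the evaluable set. The rules count patients who have a DLT, and the only consequence that Section 7.23 attaches to its criteria is replacement, from which adverse-event exits are left out. On that view the evaluability sentence is idle and the count is right. This has force: it is why a drafting slip is the likely explanation, and if the rules govern there is no bias. It does not remove the contradiction, because the sentence is the only definition of DLT evaluability and it excludes the wrong patients.

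A second reply is that the clause is aimed at patients withdrawn for a drug-related event short of a DLT, who cannot fairly be scored DLT-free. That would be sensible, and several discontinuation rows in Table 8.31 can apply below Grade 4. The sentence does not say it, however. It covers any drug-related adverse event.

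A third reply is that the trigger is narrow, and this largely stands. After a DLT the plan is to stay on treatment: "Patients who experience DLTs will be dose reduced to the next lower dose level". Table 8.31 mostly holds and restarts. Some rows, such as Grade 4 rash or Grade 4 allergic reaction, do say "Discontinue lenalidomide study drug and go to follow-up and event monitoring", and Section 8.3 adds: "If drug must be discontinued, the patient comes off treatment and goes to follow-up per Section 4.0". Whether such a patient has been withdrawn from the study in the sense of Section 7.23 is not defined.

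Two stronger arguments that a reader might draw do not hold. Section 7.22 defines a DLT but states no counting rule. Section 16.14 applies a generic DLT probability to the Section 7.2 design, so it would look the same if p were defined among evaluable patients. Neither is independent evidence of a contradiction. Nor do the documents support a fear that sites would classify the same patient differently. No section has sites applying the 3+3 rule. The sponsor's project manager controls phase I places, and group accrual pauses while a cohort is evaluated.

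**Conclusion.** The contradiction is real and should be corrected, because it concerns the count that sets the phase I primary result. The conflict is between the evaluability sentence on one side and, on the other, the 3+3 rules, Section 16.12, Sections 13.6 and 16.11, and SAP 8.1.

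Its numerical size depends on how the sentence is applied and on an f that the documents do not supply. Under the reading closest to the text, the effect is small and conservative: at a 40% DLT rate, 0.31 falls to 0.30 to 0.29. The shifts towards escalation, to 0.33 to 0.43 or 0.34 to 0.49, need both an assumed f of 5% to 25% and a handling rule that Section 7.23 does not state.

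A reader might infer that the plan builds in a large bias towards escalation, or that an MTD has already been set too high. The documents do not support either inference. f may be low, since most DLTs lead to a hold or a dose reduction, and nothing shows that any patient was misclassified.

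**What to change.** Reword the evaluability sentence in Section 7.23 along these lines:

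> A patient with a Cycle 1 DLT as defined in Section 7.22 is always evaluable and counts as a DLT in the 3+3 rules, whether or not later withdrawn. A patient without a DLT whose Cycle 1 is incomplete for a cause that is not toxicity is inevaluable and is replaced (Sections 13.6 and 16.11).

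Two matters are for the sponsor to settle in the same amendment:

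- Whether the condition that the patient has taken both drugs still applies to a patient with a DLT. The wording above would otherwise drop it silently.
- How a toxicity exit that is not a DLT is counted, so that Section 7.23 agrees with Sections 13.6 and 16.11 and SAP 8.1.

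The cost is a short wording amendment. The 3+3 rules, the Section 16.14 table and the sample size of at most 111 patients stay as they are. Replacement of non-toxicity exits is already provided for. The change concerns counting only and alters no dose or treatment rule.

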13.4 Criteria for Patient Withdrawal

Patients may be withdrawn from the study for the following reasons:

- Progressive multiple myeloma
- Patient withdraws consent to continue in the trial
- Patient develops an intercurrent illness that precludes further participation, or requires a prohibited concomitant treatment
- The Investigator withdraws the patient in the patient's best interests
- Patient is lost to follow-up (defined as the inability to contact the patient on 3 separate occasions over a period of 2 weeks)
- Administrative reasons (e.g., the patient is transferred to hospice care)
- An adverse event, which in the opinion of the Investigator, precludes further trial participation
- Pregnancy
- Closure of study by PrECOG

- 13.5 All attempts should be made to complete the End of Study procedures if a patient withdraws from the trial early.
- 13.6 **Phase I:** If a patient fails to complete one cycle of treatment for reasons other than toxicity, the patient will be regarded as inevaluable and will be replaced.
- 13.7 Patients who develop progressive disease while receiving therapy will go to the event-monitoring phase.
- 13.8 Patients who go off protocol treatment for reasons other than PD will go to the event-monitoring phase.
- 13.9 Patients who are in sCR, CR, VGPR, PR, or SD (or usCR, uCR, uVGPR, uPR) may have stem cells harvested at any time after 4 cycles at the discretion of the Investigator. If the patient is continued on therapy, lenalidomide and dexamethasone may be discontinued during the harvest period and the dates of cessation and resumption recorded.

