16.0 Statistical Considerations and Methodology

16.1 Study Design: This phase I/II study involves three single arm phase I trials designed to determine the MTD and toxicity of lenalidomide in the treatment of multiple myeloma in three groups of patients defined by renal dysfunction. Once an MTD is determined within a group, an additional 15 patients will be accrued within the group and treated with the MTD as part of the phase II study to assess efficacy of lenalidomide and dexamethasone in the treatment of multiple myeloma. The 6 phase I patients treated at the MTD plus 15 additional patients accrued in each group will be combined (total = 63 patients) to assess efficacy using a one-stage design.

The first phase I study enrolls patients with moderate renal dysfunction (Group A); the second one enrolls patients with severe renal dysfunction (Group B); and the third one enrolls patients with ESRD renal dysfunction (Group C). Groups A, B, and C have a maximum of 3, 4, and 4 dose levels respectively. The MTD for each group will be determined concurrently.

16.11 Sample Size: **Phase I:** For Group A, the study may involve a maximum of 18 patients (6 for each of the 3 dose levels) but would likely require 15 patients (3 at the first dose level, 6 for the dose level prior to the MTD, and 6 at the MTD). For Group B, the study may involve a maximum of 24 patients (6 for each of the 4 dose levels) but would likely require 18 patients (3 at the first 2 dose levels, 6 for the dose level prior to the MTD, and 6 at the MTD). For Group C, the study may involve a maximum of 24 patients (6 for each of the 4 dose levels) but would likely require 18 patients (3 at the first 2 dose levels, 6 for the dose level prior to the MTD, and 6 at the MTD). **Phase II:** Each group will accrue an additional 15 patients at the MTD. **Overall:** Therefore, overall, the study needs a maximum of 111 patients, and an expected number of 96 patients.

In addition, the protocol allows replacement of patients in phase I who withdraw before completing cycle 1 for reasons other than toxicity.

16.12 MTD Determination: MTD is defined as the dose level below the lowest dose that induces dose-limiting toxicity in at least one-third of patients (at least 2 of a maximum of 6 new patients). MTD will be determined independently for each group as outlined in Section 7.2.

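### Read literally, Protocol 7.23 drops a subject with a Cycle 1 DLT from the DLT denominator, unreplaced, if that subject is withdrawn from the study for it

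*Protocol*

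**What the plan says.** Protocol 7.23 sets two conditions for DLT evaluability. The subject must have taken each drug at least once in Cycle 1, and must "have not been withdrawn from the study prior to Cycle 2 secondary to a drug related AE". If a subject leaves without meeting these conditions "for reasons other than adverse events, the subject will be replaced in that cohort". Nothing is said about replacing a subject who leaves because of an adverse event.

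Protocol 13.6 puts it differently. If a Phase I patient does not finish one cycle "for reasons other than toxicity, the patient will be regarded as inevaluable and will be replaced". Protocol 16.11, repeated in SAP 8.1, agrees with 13.6: "the protocol allows replacement of patients in phase I who withdraw before completing cycle 1 for reasons other than toxicity".

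The escalation rules in 7.23 work on cohorts of three and six. For example: "If exactly 0/3 experience a DLT, then proceed to the next higher dose level". Protocol 7.22 lists the DLTs, which include a related "Other non-hematologic Grade 4 or higher adverse event not present prior to starting therapy or not due to underlying cause". Protocol 13.4 includes among the grounds for withdrawal: "An adverse event, which in the opinion of the Investigator, precludes further trial participation". SAP 8.5 defines ITT, safety and efficacy populations, but no DLT-evaluable set.

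**The concern.** In an MTD trial, the subject taken off study for drug toxicity is the one who carries the signal. The second condition in 7.23 makes that subject non-evaluable, and the replacement sentence leaves the place empty. The wording looks like a drafting slip, but it is the operative definition, and nothing in 7.22 or the SAP overrides it.

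The MTD in each renal group is the Phase I primary objective, and the chosen dose then goes to 15 further patients per group (16.1). According to the footnotes to the 7.21 tables, on 3 November 2010 only level 1 was complete and level 2 was open in every group, so most escalation decisions were still to come. Two people applying 7.23 and 13.6 to the same cohort could reach different decisions.

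**Working it through.** **Step 1: the plan's own table.** Section 16.14 gives the probability of escalating past a dose level. For true DLT rate p, escalation needs 0/3, or 1/3 followed by 0/3:

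P(escalate) = (1−p)³ + 3p(1−p)² × (1−p)³ = (1−p)³ + 3p(1−p)⁵

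| p | 10% | 20% | 30% | 40% | 50% |
|---|---|---|---|---|---|
| Computed | 0.906 | 0.709 | 0.494 | 0.309 | 0.172 |
| Stated in 16.14 | 0.91 | 0.71 | 0.49 | 0.31 | 0.17 |

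The table is correct. It assumes full cohorts of three and six with every DLT counted.

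**Step 2: the two sections side by side.**

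| Subject in Cycle 1 | Literal 7.23 | 13.6, with 16.11 and SAP 8.1 |
|---|---|---|
| Withdrawn from the study for a drug-related AE, including a DLT | Not evaluable; no provision for replacement | Not replaced; by implication evaluable |
| Leaves for a non-AE reason after taking both drugs once | Evaluable and not replaced, if the criteria are sufficient | Inevaluable and replaced |

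**Step 3: what this does to a decision.** Suppose one subject with a DLT is withdrawn for it and removed.

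| All treated subjects | Decision | After removal |
|---|---|---|
| 1/3 | Enter three more | 0/2: no entry |
| 2/3 | Stop escalation | 1/2: no entry |
| 1/3, then 1/3, so 2/6 | Stop escalation | 1/5: no entry |

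The MTD definition in 16.12 turns on one-third of patients. For the last row, 2/6 = 33% reaches that threshold and 1/5 = 20% does not.

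**Step 4: can a DLT end in withdrawal?** Related grade 4 rash and related grade 4 allergic reaction are DLTs under 7.22, and Table 8.31 stops lenalidomide permanently for both. That sits badly with the 7.23 sentence "Patients who experience DLTs will be dose reduced to the next lower dose level". Whether such a stop is also withdrawal from the study is not settled. Section 8.3 and Table 8.31 send the patient to follow-up. Section 13.4 allows withdrawal for an AE. Section 13.4 also lists progressive myeloma as a withdrawal ground, while 13.7 sends progressing patients to event monitoring, so being in event monitoring does not show that a patient was not withdrawn.

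**Step 5: illustration only.** Let w be the share of DLT subjects who are withdrawn. The documents give no value for w; those below are assumptions. The DLT rate among evaluable subjects becomes p(1−w)/(1−pw). At p = 0.30:

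- w = 10%: 0.270/0.970 = 0.278
- w = 25%: 0.225/0.925 = 0.243
- w = 50%: 0.150/0.850 = 0.176

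If a team nevertheless enrolled until it had full evaluable cohorts, putting these rates into the Step 1 formula would move the escalation probability at a true 30% from 0.49 to 0.54, 0.61 or 0.76. Section 7.23 does not provide for that refilling after an AE withdrawal.

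**The case against.** The strongest answer is that the escalation rules do not use evaluability as their denominator. Section 7.23 speaks of subjects treated at the dose level and of patients who experience a DLT, and 16.12 counts new patients. On that wording a treated patient with a grade 4 rash counts. Section 7.23 also expects DLT patients to be dose-reduced, and 13.4 is permissive. All of this stands as mitigation. But if the DLT is counted regardless, the evaluability clause does no useful work and should go.

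A count such as 0/2 might be treated as an unfinished cohort, since the rules ask for at least three subjects. That is a workable reading, but it refills the cohort without counting the DLT. Individual safety assessment (7.23) and optional suspension of accrual (16.4) remain available, but neither says who is evaluable.

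A reader might infer that the early non-toxicity dropout is treated inconsistently on any reading. The documents do not support that: 7.23 states what a subject must satisfy, so its criteria can be read as necessary conditions to which 13.6 adds another. The inconsistency arises only if they are taken as sufficient. Likewise, 13.6 does not say outright that toxicity dropouts are evaluable; that is its implication.

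A reader might also want to add to the DLT list the events below grade 4 for which Table 8.31 requires permanent discontinuation. Section 7.22 deliberately sets grade 4 as the threshold for other non-hematologic events. Changing it after level 1 was completed in all groups would mix endpoint definitions across dose levels.

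**Conclusion.** The concern holds in a limited form and should be fixed. Taken literally, 7.23 removes, without replacement, a subject with a Cycle 1 DLT who is withdrawn from the study for it. That runs against the implication of 13.6, 16.11 and SAP 8.1 and against the full-cohort assumption behind 16.14. The changed counts in Step 3 are exact, but only for a DLT subject who is actually withdrawn from the study, not merely taken off lenalidomide.

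No overall effect size can be claimed. The frequency of such withdrawals is not given and may be low, and a sensible team would probably count the DLT anyway. A reader might infer that the escalation probabilities in 16.14 are wrong, or that they are inflated by a known amount. Neither is supported: the table reproduces, and every shifted figure in Step 5 rests on an assumed w.

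**What to change.** In 7.23, delete the condition "have not been withdrawn from the study prior to Cycle 2 secondary to a drug related AE" and put three statements in its place:

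1. Any treated subject with a Cycle 1 DLT is evaluable, counts as a DLT and is not replaced.
2. A subject without a DLT who fails to complete Cycle 1 for a non-toxicity reason is inevaluable and is replaced, as in 13.6.
3. A subject who stops in Cycle 1 for a toxicity that is not a DLT is not replaced, stays in the denominator, and is followed for DLT to the end of the Cycle 1 window.

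Use the same definition for a DLT-evaluable set in SAP 8.5. Check the Cycle 1 records of completed cohorts to confirm that no toxicity withdrawal was excluded; Protocol 1.7 reports 15 subjects enrolled by 9 November 2010. Leave the DLT definition in 7.22 and the actions in Table 8.31 unchanged.

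The cost is one deleted clause, three sentences, one SAP definition and a short record check. Escalation may occasionally stop earlier. A few non-toxicity dropouts will be replaced, which 16.11 already allows. The 16.14 table then applies as printed.
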